TEAE	treatment-emergent adverse event
t_{max}	time to corresponding Cmax
ULN	upper limit of normal
VAS	visual analogue scale
WBC	white blood cell
<lloq< td="">below the lower limit of quantification	</lloq<>	below the lower limit of quantification

1 INTRODUCTION

Ra Pharmaceuticals, Inc. is developing RA101495, a subcutaneously–administered cyclic peptide that inhibits the cleavage of complement component 5 (C5), for the treatment of paroxysmal nocturnal hemoglobinuria (PNH).

Study RA101495-01.201 is a multicenter, open-label, uncontrolled study to evaluate the safety, tolerability, efficacy, pharmacokinetics and pharmacodynamics of RA101495 in subjects with PNH.

The study will enroll two separate cohorts based on prior eculizumab treatment history.

- Cohort A (Naïve) will include subjects who have not received eculizumab for treatment of PNH
- Cohort B (Switch) will include subjects who have received treatment with eculizumab for at least 6 months prior to Screening.

The planned enrollment is approximately 8-12 subjects in Cohort A and approximately 6-8 subjects in Cohort B, for a total of up to 20 subjects.

This Statistical Analysis Plan (SAP) describes data-handling and statistical procedures to be used for the analysis and reporting of efficacy and safety data collected under Study RA101495-01.201 (version 1.1 20 October 2016) and presented in the clinical study report (CSR). They are based on those presented in Section 13 of the study protocol. Any post-hoc or exploratory analyses not specified in this SAP will be identified as such when they are presented in the CSR. This SAP has been developed and finalized prior to locking the clinical database.

The SAP was written in accordance with the recommendations outlined in the International Conference on Harmonisation (ICH) E9 Guideline entitled "Guidance for Industry: Statistical Principles for Clinical Trials" and the most recent ICH-E3 Guideline, entitled "Guidance for Industry: Structure and Content of Clinical Study Reports."

2 STUDY SUMMARY

2.1 STUDY OBJECTIVES

The objectives of the study are

- To assess the safety and tolerability of RA101495 in subjects with PNH
- To assess preliminary efficacy of RA101495 in subjects with PNH

• To assess the pharmacokinetics (PK) and pharmacodynamics (PD) of RA101495 in subjects with PNH.

2.2 STUDY DESIGN

Study RA101495-01.201 is a multicenter, open-label, uncontrolled study to evaluate the safety, tolerability, efficacy, pharmacokinetics and pharmacodynamics of RA101495 in subjects with PNH.

The study will enroll two separate cohorts based on prior eculizumab treatment history.

- Cohort A (Naïve) will include subjects who have not received eculizumab for treatment of PNH
- Cohort B (Switch) will include subjects who have received treatment with eculizumab for at least 6 months prior to Screening.

The planned enrollment is approximately 8-12 subjects in Cohort A and approximately 6-8 subjects in Cohort B, for a total of up to 20 subjects.

Cohort A will commence enrollment prior to Cohort B. Cohort B will not be opened until safety and efficacy data from at least 2 subjects completing the Week 2 visit in Cohort A have been reviewed by the Sponsor and Study Investigators, and evidence of hemolysis suppression is demonstrated.

The study includes an 8-week screening period and a 12-week Treatment Period. During the Treatment Period, subjects will return to the clinic weekly for the first 4 weeks followed by visits every 2 weeks to evaluate safety, tolerability, efficacy, PK and PD. Additional assessments will include immunogenicity, Quality of Life (QOL) questionnaires, biomarker samples, and optional pharmacogenomics. Safety assessments include physical exam, vital signs, electrocardiogram (ECG), clinical laboratory tests, and adverse events (AEs).

At the conclusion of the Treatment Period subjects who complete the study and are demonstrating benefit will have the option to enroll in an extension study to continue receiving treatment with RA101495. Alternatively, they may opt to receive standard-of-care treatment off study, after consultation with their treating physician. If the subject withdraws early from the RA101495-01.201 study for any reason, he/she will not be eligible for the extension study.

From the Week 2 visit onwards, if a subject has not achieved an adequate response (defined as a lactate dehydrogenase [LDH] <1.5 x ULN), and following evaluation of safety and tolerability data by the investigator and the medical monitor, the dose should be escalated to 0.3 mg/kg daily. The dose may also be escalated to 0.3 mg/kg daily at any time in the event of an overt breakthrough hemolysis episode (e.g. hemoglobinuria).

The total duration of study participation for all subjects will include a Screening Period of up to 8 weeks and a 12-week Treatment Period for a total of up to 20 weeks.

2.2.1 Number of Patients

Up to 20 subjects will be enrolled in the study in two cohorts:

- Cohort A (Eculizumab Naïve): approximately 8-12 subjects
- Cohort B (Eculizumab Switch): approximately 6-8 subjects.

2.2.2 Randomization and Blinding Procedures

This is an open-label single-arm uncontrolled study.

2.2.3 Safety Assessments

Safety assessments include physical examination, vital signs, electrocardiogram, *Neisseria meningitidis* testing and prophylactic treatment, adverse events, blood chemistry and hematology, urinalysis, pregnancy test, PNH clone and testing for immunogenicity.

2.2.3.1 Physical Examination

Physical examinations will include the following assessments:

- General inspection
- Weight (kg) and height (height in cm to be collected at screening visit only)
- Examination of the injection site and draining nodes
- Head/ears/eyes/nose/throat examination
- Mucosal examination for icterus
- Cardiac examination
- Auscultation of lungs
- Abdominal examination (liver, spleen, and lower abdomen)
- Assessment for neurological deficits
- Musculoskeletal assessment

Any abnormalities found will be recorded in the eCRF.

2.2.3.2 Vital Signs

Vital signs (heart rate, body temperature, and blood pressure) will be measured in the sitting position after resting for at least 5 minutes.

2.2.3.3 Electrocardiogram

ECGs will be assessed as normal or abnormal by the investigator; any abnormal findings will be described in the eCRF and the investigator will assess clinical significance.

2.2.3.4 Neisseria meningitidis Testing

All subjects must have a negative result for *Neisseria meningitidis* colonization via a throat swab prior to study entry.

2.2.3.5 Adverse Event Recording

An AE is any untoward medical occurrence in a subject administered a pharmaceutical product and which does not necessarily have a causal relationship with this treatment. An AE can therefore be any unfavorable and unintended sign (including a clinically significant abnormal laboratory finding, for example), symptom, or disease temporally associated with the use of a medicinal product, whether or not considered related to the medicinal product.

The following are not considered to be AEs despite requiring hospitalization:

- Pre-existing conditions that, in the opinion of the investigator, did not worsen or progress during study participation
- Routinely scheduled procedures or treatment
- Elective procedures that had been scheduled prior to study participation (i.e. signing of the informed consent form (ICF))

A Serious adverse event (SAE) is any untoward medical occurrence that:

- results in death
- is life-threatening (note that this refers to an event in which the subject was at risk of death at the time of the event; it does not refer to an event that hypothetically might have caused death if it were more severe)
- requires hospitalization or prolongation of existing hospitalization
- results in persistent or significant disability/incapacity
- results in a congenital anomaly/birth defect

An SAE may also be any other important medical event that may not be immediately life-threatening or result in death or hospitalization, but may jeopardize the subject or require intervention to prevent one of the other outcomes listed in the definition above. Examples of such events include intensive treatment in an emergency room or

at home for bronchospasm, hyperkalemia, or convulsions that do not result in a formal hospitalization.

Elective hospitalizations scheduled prior to study participation (i.e. signing of the ICF) should not be reported as SAEs.

2.2.3.6 Blood Chemistry and Hematology

Clinical chemistry and hematology analytes to be collected are identified in Table 1 and should be performed as specified in the Time and Events (Table 2).

Table 1: Clinical Chemistry, Hematology, and Coagulation Analytes

Clinical Chemistry	Hematology		
alanine aminotransferase (ALT)	free hemoglobin		
albumin	haptoglobin		
alkaline phosphatase (ALP)	hematocrit		
amylase	hemoglobin		
aspartate aminotransferase (AST)	mean corpuscular hemoglobin (MCH)		
bicarbonate	mean corpuscular hemoglobin concentration		
bile acids	(MCHC)		
bilirubin (total, direct, and	mean corpuscular volume (MCV)		
indirect)	platelet count		
blood urea nitrogen (BUN)	RBC count		
calcium	reticulocyte count and %		
chloride	white blood cell (WBC) count and differential		
creatinine	(%)		
gamma-glutamyl transferase	 basophils 		
(GGT)	 eosinophils 		
glomerular filtration rate MDRD ^a	lymphocytes		
glucose	monocytes		
lactate dehydrogenase (LDH)	 neutrophils 		
lipase			
potassium	Coagulation		
sodium	international normalized ratio (INR)		
total protein	prothrombin time (PT)		
uric acid	fibrinogen		
	activated partial thromboplastin time (APTT)		
	Other		
	C-reactive protein (CRP)		
	creatine phosphokinase (CPK)		

a: presented in listings only (not summarized).

2.2.3.7 Urinalysis

A urinalysis will be performed to measure pH, specific gravity, protein (qualitative), glucose (qualitative), ketones (qualitative), bilirubin (qualitative), urobilinogen, occult blood, hemoglobin, RBC casts, bilirubin crystals, uric acid crystals, and cells (squamous epithelial, transitional epithelial, and tubular epithelial). A microscopic examination will be performed, if necessary. Hemoglobinuria will be assessed using a urine colorimetric scoring system (a 0-10 point scale).

The following urinalysis parameters will be summarized: Erythrocytes, specific gravity, and pH. All other urinalysis assessments will be presented in listings.

2.2.3.8 Pregnancy Test

A serum pregnancy test for human chorionic gonadotropin will be performed on female subjects of childbearing potential at Screening.

A urine dipstick pregnancy test (human chorionic gonadotropin) will be performed on female subjects of childbearing potential at Day 1 pre-dose and Day 29, Day 57, and Day 84 (End of Study).

2.2.3.9 PNH Clone

Blood sample for measurement of PNH close size will be collected at Screening (i.e., most recent PNH clone size prior to study entry), Day 29, Day 57, and Day 84 (or End-of-Study Visit). PNH close size will be determined by peripheral blood flow cytometry analysis (RBCs and granulocytes).

2.2.3.10 Immunogenicity

Blood samples for ADAs will be collected prior to dosing on Day 1 and on Day 29, Day 57, and Day 84 (or at the End-of-Study Visit) in all enrolled subjects. Samples will be sent to a central laboratory to determine the presence or absence of antibodies against RA101495 using a validated assay.

Detailed instructions regarding sample collection, processing, and shipping will be provided in a separate laboratory manual.

2.2.4 Efficacy Assessments

Efficacy assessments include the measurement of serum LDH levels as a measure of intravascular hemolysis. Additional assessments will include laboratory assessments of total bilirubin, total hemoglobin, free hemoglobin, haptoglobin, reticulocytes, and hemoglobinuria.

2.2.5 Exploratory Assessments

Exploratory endpoints include:

- Changes from baseline in QOL questionnaires
 - European Organization for Research and Treatment of Cancer-Quality of Life Questionnaire (EORTC QLQ-C30)
 - Functional Assessment of Chronic Illness Therapy-Fatigue Scale (FACIT-Fatigue)
 - o EuroQol 5D (EQ-5D)
- Treatment satisfaction questionnaire

2.2.6 Pharmacodynamic Assessments

The pharmacodynamics (PD) assessments include: sheep red blood cell (sRBC), Wieslab enzyme-linked immunosorbent assay (ELISA), and C5. Blood samples for the PD assessments occur at each study visit (except the screening visit).

Blood samples for RA101495 PD occurs at the following time points in relationship to the first dose of RA101495: pre-dose (within 1 hour before first dose administration) and at 1, 3, and 6 hours post-dose on Day 1.

For subjects who have a dose increase to 0.3 mg/kg, samples for PD should be collected at pre-dose Day 1 of the new dose.

2.2.7 Pharmacokinetic Assessments

Blood samples for RA101495 pharmacokinetics (PK) occurs at the following time points in relationship to the first dose of RA101495: pre-dose (within 1 hour before first dose administration) and at 1, 3, and 6 hours post-dose on Day 1.

For subjects who have a dose increase to 0.3 mg/kg, samples for PK should be collected at pre-dose Day 1 of the new dose.

On other clinic visit days, PK and PD samples should be collected prior to administration of RA101495.

For subjects in Cohort B only, blood samples for PK of eculizumab should be collected at screening, Day 1, Day 15, Day 29, and Day 43 (at 2-week, 4-week, and 6-week) visits. The sample should be collected prior to administration of RA101495.

2.2.8 Schedule of Assessments

The following is the time and events table

Table 2: Time and Events Table

Phase	Screening Period				Tr	eatment	Period			
Study Week →	-8 to 1	0	1	2	3	4	6	8	10	12 (End of Study)
Study Day ^a →	-56 to -1	1 ± 2 ^b	8 ± 2	15 ± 2	22 ± 2	29 ± 2	43 ± 4	57 ± 4	71 ± 4	84 ± 4
Study Procedure ↓										
ICF process and signed ICF	X									
Review eligibility criteria	X	X								
Medical history and demographics	X									
Prior and concomitant medications	X	X	X	X	X	X	X	X	X	X
Physical examination	X	X				X				X
Height and weight ^c	X	X				X				X
Vital signs	X	X				X				X
Electrocardiogram	X	X				X				X
Neisseria throat swab ^d	X									
Neisseria vaccination ^d		X				X				
Ciprofloxacin treatment ^d		X	X	D14						
Blood chemistry ^e	X	X	X	X	X	X	X	X	X	X
Hematology	X	X	X	X	X	X	X	X	X	X
Coagulation ^f	X	X	X	X	X	X	X	X	X	X
Urinalysis	X	X	X	X	X	X	X	X	X	X
PNH clone size	X					X		X		X

Phase	Screening Period				Tr	eatment	Period			
Study Week →	-8 to 1	0	1	2	3	4	6	8	10	12 (End of Study)
Study Day ^a →	-56 to -1	1 ± 2 ^b	8 ± 2	15 ± 2	22 ± 2	29 ± 2	43 ± 4	57 ± 4	71 ± 4	84 ± 4
Pregnancy test ^g	X	X				X		X		X
Adverse events		X	X	X	X	X	X	X	X	X
Assessment of injection site reactions ^h		X	X	X	X	X	X	X	X	X
Pharmacokinetics RA101495i		X	X	X	X	X	X	X	X	X
Pharmacokinetics eculizumab ^j	X	X		X		X	X			
Pharmacodynamics RA101495 ⁱ		X	X	X	X	X	X	X	X	X
Anti-drug antibody ^k		Xk				X		X		X
Quality of life questionnaires										
EORTC-QLQ-C30		X				X		X		X
FACIT-Fatigue		X				X		X		X
EQ-5D		X				X		X		X
Treatment satisfaction assessment										X
Additional biomarker samples ⁱ		X	X	X	X	X	X	X	X	X
Pharmacogenomic analysis (optional) ¹		Xl								
Electronic diary training and dispensation, collection at End of Study		X								X
RA101495 administration ^m		X	X	X	X	X	X	X	X	X
RA101495 dispensing and return ⁿ		X		X		X	X	X	X	X

Abbreviations: EORTC-QLQ-C30=European Organization for Research and Treatment of Cancer-Quality of Life Questionnaire; EQ-5D=EuroQol 5D questionnaire; FACIT-F=Functional Assessment of Chronic Illness Therapy-Fatigue Scale; ICF=informed consent form; LDH=lactate dehydrogenase; NA=not applicable; PD=pharmacodynamic; PK=pharmacokinetic.

- Study visits have a Visit window of ± 2 days after the actual planned Visit day for the first 4 weeks, and ± 4 days from week 6 to week 12.
- For Cohort A (Naïve) subjects, the Day 1 Visit may be scheduled at any time after Screening and confirmation of eligibility. For Cohort B (Switch) subjects, the Day 1 Visit should be scheduled to coincide with the next scheduled dose of eculizumab (i.e. 14 ±2 after from the last eculizumab dose). Eculizumab should NOT be administered at the Day 1 Visit or at any time thereafter during the study.
- Height will be measured only at the Screening Visit.
- d. All subjects must have a negative throat swab for *Neisseria meningitidis* infection for eligibility. All subjects in Cohort A must be vaccinated against Neisseria meningitidis and should have a booster as indicated by standard of care. All subjects in Cohort A must receive ciprofloxacin to be taken orally on Days 1 to 14. All Cohort B subjects must have documentation of prior *Neisseria meningitidis* vaccination (and booster if appropriate) prior to study entry.
- Including LDH for primary efficacy endpoint
- Coagulation tests should be performed, according to standard practice, on all subjects taking anticoagulant therapy.
- For all female subjects of childbearing potential, a negative serum pregnancy test must be documented at the Screening Visit and a negative urine pregnancy test must be documented at the Day 1 Visit prior to dosing. All other pregnancy tests will be urine.
- h. The injection site should be assessed at each clinic visit through Day 84 (End of Study).
- Blood samples for PK and PD and additional biomarker sampling at the following time points in relationship to the first dose of RA101495: pre-dose (within 1 hour before first dose administration) and at 1, 3, and 6 hours post-dose on Day 1. For subjects who have a dose increase to 0.3 mg/kg, samples for PK and PD should be collected at pre-dose Day 1 of the new dose, see footnote j. On clinic visit days, PK and PD samples should be collected prior to administration of RA101495.
- For subjects in Cohort B only, blood samples for PK of eculizumab should be collected at screening, Day 1, Day 15, Day 29, and Day 43. (at 2-week, 4week, and 6-week) Visits. The sample should be collected prior to administration of RA101495.
- Blood sample for ADA on Day 1 must be obtained prior to dosing of RA101495.
- Blood sample for optional pharmacogenomic testing must be obtained on Day 1.
- On clinic visit days, the study drug RA101495 should be administered after blood samples for PK and PD are collected.
- Prefilled syringes containing RA101495 will be dispensed every 2 weeks. Subjects will also receive a secure container to dispose of used syringes at each visit and should return the used container containing all used syringes to each study visit. All study drug (syringes) and disposal containers must be returned to the site at the last study visit. Dosing on study visit days will be held until the completion of the PK and PD sample blood collection has been completed.

3 STATISTICAL METHODS

3.1 General Methods

3.1.1 Computing Environment

All statistical analyses will be performed using SAS® Version 9.1.3 or higher for Windows.

3.1.2 Reporting of Numerical Values

All clinical study data will be presented in patient data listings. Descriptive statistics (n, mean, standard error of the mean, standard deviation, median, minimum, and maximum) will be calculated by treatment group for continuous variables. Confidence intervals will be provided where appropriate. For continuous endpoints, the confidence interval for the mean will be based on the t-distribution (e.g., CLM in the SAS Proc Means procedure).

Frequencies and percentages will be presented by treatment group for categorical and ordinal variables. If there are missing values, the number of missing values will be presented, but without a percentage and the number of non-missing values used as the denominator.

Means, medians, standard deviations, standard error of the mean, and confidence intervals will be reported to one decimal place more than the data reported on the CRF or by the laboratory/vendor. Minimum and maximum will be reported to the same number of decimal places displayed on the CRF or by the laboratory/vendor. P-values will be reported to 4 decimal places.

3.1.3 Baseline Value and Change from Baseline

Baseline value is defined as the most recent non-missing value obtained immediately prior to administration of first dose (i.e., generally the study day 1 assessment which occurs pre-dose).

However, for Cohort A (Eculizumab Naïve) subject's baseline LDH will be the average of the Study day 1 and Screening period values.

Change from baseline will be calculated by subtracting the baseline value from the post-dose assessment for each patient (i.e. post-dose – baseline). Percent change from baseline will be calculated as 100×change score/ baseline score.

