10.1.3 DOSING SCHEDULE

For Cohort A (Naïve) subjects, the Day 1 Visit may be scheduled at any time after Screening and confirmation of eligibility.

For Cohort B (Switch) subjects, the Day 1 Visit should be scheduled to coincide with the next scheduled dose of eculizumab (i.e. 14 ± 2 days after from the last eculizumab dose). Eculizumab should NOT be administered on the Day1 Visit or at anytime thereafter during the study.

Subjects in Cohort A (Naïve) and Cohort B (Switch) will receive a loading dose of 0.3 mg/kg dose of RA101495 on Day 1, which will be administered during the study Visit by the site staff. During the remainder of the Treatment Period, subjects will self-administer the daily dose (0.1 mg/kg or 0.3 mg/kg) every 24 hours at approximately the same time each day. On days of the scheduled study Visit at the investigator site, the dose must be administered after the blood work is completed at the investigator site.

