11.1.2 DISEASE AND PRIOR TREATMENT HISTORY

A detailed history of PNH for a minimum of 6 months prior to Screening will be obtained, including (but not limited to) the following data: date of diagnosis, PNH clone size at diagnosis (if available), history of thrombotic events, history of transfusions, and history of PNH-specific prior therapy (e.g. immunosuppressives, anticoagulants, associated bone-marrow disorders).

For Cohort B (Switch) subjects, the date ecilizumab treatment was initiated and dose received will be documented. A dosing history for each subject (including dates and all dosage changes for a minimum of 6 months prior to Screening) will also be recorded.

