3.1.4 Screening Values

For the tables and figures, a patient's screening value is defined as the most recent non-missing value with a visit value of "Screening". In the listings, all values which have a visit of "Screening" will be presented.

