3.5.4 PNH Treatment History

The following PNH treatment history data will be summarized by cohort and overall.

- Eculizumab treatment history (note: Cohort B only)
 - o Age at initial eculizumab treatment

Age at initial eculizumab treatment will be calculated as (date of initial eculizumab treatment – date of birth + 1)/365.25,

Note: If the day and month are missing for date of initial eculizumab treatment, impute July 2nd, if only the day is missing impute the 15th. If the date of birth day and month are missing impute January 1st, if only the day is missing impute the 1st.

o Duration of eculizumab treatment (months)

Calculated as:

(stop date of eculizumab treatment – start date of eculizumab treatment+ 1) /(365.25/12)

Note: For stop date and start date, if the day and month are missing impute July 2^{nd} , if only the day is missing impute the 15^{th} . If corresponding duration calculation yields a negative number, impute a value of 1 day = 1/30.4375 months.

o Eculizumab dose, units and frequency will be provided in the listings.

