3.9.1 Primary Efficacy Endpoint Analysis

The primary evaluation period is from Week 6 to Week 12. The primary efficacy endpoint is the change from baseline in serum LDH levels during this period, defined as the mean of the non-missing LDH values of Weeks 6, 8, 10, and 12 minus the baseline LDH value (defined in Section 3.1.3).

The primary efficacy endpoint analysis will be a Wilcoxon signed-rank test on the change from baseline endpoints.

Summary statistics and will be provided for patient's mean LDH value, change from baseline scores, and percent change from baseline scores over the primary evaluation period.

Additionally, summary statistics for the values, change from baseline, percent change from baseline scores, and the two-sided Wilcoxon signed-rank test will be performed at each post-baseline assessment time-point.

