3.11 Sample Size Considerations

For Cohort A (Naïve) a sample size of 8 subjects yields approximately 95% power to reject the null hypothesis that the median LDH change from baseline is 0 for the

primary efficacy endpoint. This assumes a mean decrease in LDH from 2200 U/L at baseline to 327 U/L during the primary evaluation period (Weeks 6 -12) with corresponding standard deviations of 1034 U/L and 443 U/L, and a within-subject correlation estimate of 0. This yields a change from baseline mean of 1873 U/L and standard deviation of 1125 U/L. The power is based on a 2-sided Wilcoxon signed-rank test at the 0.05 significance level.

For Cohort B (Switch) a sample size of 6 subjects will yield a standard error of approximately 114 for an LDH mean change from baseline estimate. This assumes a standard deviation of 443 for the baseline and post-baseline endpoints and a within-subject correlation estimate of 0.8, which yields change from baseline standard deviation of 280 U/L.

The LDH mean and standard deviation estimates are based on the results summarized by Hillmen [2006].

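### Does Cohort B's LDH change need a companion summary from Screening, because its single baseline value falls at the end of the eculizumab cycle?

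*SAP*

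**What the plan says.** **Baseline.** SAP 3.1.3: "Baseline value is defined as the most recent non-missing value obtained immediately prior to administration of first dose", which it expects to be the Day 1 pre-dose assessment. The only exception is LDH in Cohort A (Naïve), where Day 1 and Screening are averaged. Cohort B LDH therefore keeps a single value.

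**Timing.** Protocol 8.1 and 10.1.3 set the Cohort B Day 1 Visit for when the next eculizumab infusion would be due, 14 ± 2 days after the last. On later clinic days, "the dose must be administered after the blood work is completed at the investigator site" (Protocol 10.1.3). Protocol 8.2.1 allows Screening from 2 to 56 days before Day 1 and does not tie it to the eculizumab cycle.

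**Planned summaries.** SAP 3.9.1 covers each patient's "mean LDH value, change from baseline scores, and percent change from baseline scores over the primary evaluation period". SAP 3.1.4 fixes what counts as Screening in tables and figures: the "screening value is defined as the most recent non-missing value" labelled as such. It also lists every Screening value. No section or table title plans a change from Screening. The table shells are a separate document and were not available.

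**Eculizumab data.** SAP 2.2.7: "blood samples for PK of eculizumab should be collected at screening, Day 1, Day 15, Day 29, and Day 43" (Cohort B only). Protocol 11.1.2 records a dosing history, "including dates and all dosage changes for a minimum of 6 months prior to Screening". SAP 3.5.4: "Eculizumab dose, units and frequency will be provided in the listings".

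**Inference.** Protocol 13.3.5 excludes an inferential test of the primary endpoint in Cohort B and asks for summary statistics only.

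**The concern.** Protocol 6.4 says that breakthrough hemolysis on eculizumab, where it occurs, tends to come late in the two-week cycle. Protocol 8.1.1 links that part of the interval to rising LDH. Day 1 is placed exactly there. A late-cycle excess in the Day 1 value passes one-for-one into the post-minus-baseline change. It would make the switch look more favorable, or hide a rise, compared with the subject's LDH over the whole cycle. Cohort B is small and uncontrolled, so one such subject could move the mean visibly. A Screening LDH exists for everyone, yet no planned summary uses it as an alternative reference, and nothing in the SAP sets LDH beside the cycle day on which it was drawn.

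**Working it through.** **1. The plan's own figure.** Inputs from SAP 3.11: SD 443 U/L at both times, correlation 0.8, n = 6.

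- Variance of change = 2 × 443² × (1 − 0.8) = 78,500; SD = 280.2.
- SE = 280.2/√6 = 114.4. This agrees with "6 subjects will yield a standard error of approximately 114". At n = 8 the SE is 280.2/√8 = 99.1.
- Protocol 8.1.1 prints 433 for the Week 26 SD. Using 433, the SE at n = 6 is 111.8, so the mismatch does not matter here.

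**2. Effect of a late-cycle excess.** *Assumption, with no source in the documents:* one subject's Day 1 LDH is raised by a = 300 or 600 U/L. The mean change moves by −a/n. If the planning SD does not already include the excess, it adds a²/n to the expected sample variance.

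| n | a | shift in mean | in planned SEs | SE with excess added | in those SEs |
|---|---|---|---|---|---|
| 6 | 300 | −50 | 50/114.4 = 0.44 | √(93,500/6) = 124.8 | 0.40 |
| 6 | 600 | −100 | 100/114.4 = 0.87 | √(138,500/6) = 151.9 | 0.66 |
| 8 | 300 | −37.5 | 37.5/99.1 = 0.38 | √(89,750/8) = 105.9 | 0.35 |
| 8 | 600 | −75 | 75/99.1 = 0.76 | √(123,500/8) = 124.2 | 0.60 |

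Protocol 13.3.5 also asks for the median, which moves less: about −44 and −64 U/L at n = 6 in 400,000 simulated trials (normal changes, SD 280.2). For scale, the 95% t half-width for the mean at n = 6 is 294 U/L.

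**3. What a change from Screening would show.** The difference between the two versions of the mean change is the mean of Day 1 minus Screening. Its SD is 443 × √(2(1 − r)), where r is the Screening–Day 1 correlation (assumed).

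| r | SD | SE, n = 6 | 300 in SDs | 600 in SDs |
|---|---|---|---|---|
| 0.80 | 280.2 | 114.4 | 1.07 | 2.14 |
| 0.90 | 198.1 | 80.9 | 1.51 | 3.03 |
| 0.95 | 140.1 | 57.2 | 2.14 | 4.28 |

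A mean shift of 50 to 100 U/L would be sought with an SE of 57 to 114. A gap near zero would not exclude the problem, and a non-zero gap could be ordinary variation. Screening may also fall late in a cycle, in which case the gap is near zero whatever the truth. What information there is lies in the individual subjects.

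**4. Is the individual information already planned?**

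- Screening and Day 1 LDH: SAP 3.1.2 puts all study data in listings, and SAP 3.1.4 includes every Screening value. Listings 16.2.6 (efficacy) and 16.2.12.2 (chemistry) are the natural places.
- Eculizumab concentration at both draws, with collection times: listing 16.2.8.3, summarized in table 14.2.11.4. Similar concentrations at the two draws would suggest similar points in the cycle.
- Days since last dose: SAP 3.5.4 uses the eculizumab stop date to derive duration, so the interval to Day 1 is a subtraction, and the protocol already confines it to 12–16 days. Dosing dates around Screening are recorded under Protocol 11.1.2.
- Mean LDH over Weeks 6–12 does not depend on any baseline. If the LDH table carries a Screening row, subtracting its mean gives the mean change from Screening for the same subjects.

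The missing items are the median, SD and SE of that change, and one display that puts these columns together.

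**The case for a change.** The strongest case for acting is that the protocol itself identifies late cycle as the time when eculizumab control is weakest. A single draw there is then compared with a mean of up to four on-treatment values. Cohort A gets an averaged LDH baseline, and the SAP gives no reason for treating Cohort B differently. Cohort B has no LDH entry threshold, so its Screening value is not selected high. The sponsor sees open-label data as they accrue (SAP 3.10), and SAP 1 labels unplanned analyses post hoc, so a check counts for more if written down beforehand. SAP 3.9.1 does not confine its Wilcoxon test to Cohort A, so a p-value could rest on this baseline. The cost would be a sentence and a few table rows.

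The facts stand: one late-cycle baseline value, no planned change from Screening, and no column of cycle days. The inference to a needed change does not. Before first dose, Cohort A is untreated and has no eculizumab cycle, so averaging two values is natural. In Cohort B the two values may come from different cycle days, and averaging would only halve a Day 1 excess that Screening does not share. Eliminating end-of-cycle breakthrough is a stated expectation of daily dosing (Protocol 6.4), so part of any late-cycle difference belongs to the effect of interest. Pre-specification adds little when the check cannot resolve the shift and the raw pairs are listed anyway. The scope of the Wilcoxon test is a separate matter, and the protocol's position on it is clear.

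**Conclusion.** No change to the plan is needed. Day 1 is a fair choice of baseline: it is the last value on eculizumab, its place in the cycle is standardized, and like the later draws it precedes that day's RA101495 dose. Screening is less standardized on the first two counts. The Cohort B result is descriptive under the protocol, and with 6–8 subjects an analyst can read the pairs of LDH values and concentrations straight from the planned listings. A side-by-side display would be a convenience and would alter no main result.

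The size rests on assumption. An excess of 300 to 600 U/L in one subject moves the mean change by 50 to 100 U/L at n = 6 (0.44 to 0.87 of the planned SE) and by 37.5 to 75 U/L at n = 8 (0.38 to 0.76). The documents give neither the size nor the frequency of such an excess; Protocol 6.4 speaks only of some patients. The conclusion also assumes that the listings carry what SAP 3.1.2 and 3.1.4 promise, since the shells could not be checked.
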